Self-administered lidocaine gel for pain-control
during cervical preparation for dilation and
evacuation: A randomized controlled trial

NCT02852434

07/18/2016

Stanford University
Stanford, California 94305

Self-administered lidocaine gel for pain-control during cervical preparation for dilation and evacuation: A randomized controlled trial

Background

Methods of cervical preparation prior to dilation and evacuation (D&E) after 16 weeks gestation vary. Most commonly, providers in the United States use misoprostol, mifepristone, osmotic dilators, and laminaria—either independently or in conjunction with each other. Efforts to research the use of mifepristone and misoprostol alone for cervical preparation are motivated by the desire to decrease discomfort associated with cervical preparation and increase access to abortion at later gestations by eliminating the use of laminaria or osmotic dilators. To compliment these efforts, more research is needed to investigate methods of pain control for cervical preparation with osmotic dilators and laminaria to decrease patient discomfort. Women report laminaria and osmotic dilator placement to be painful.

Pain control trials in the abortion literature often focus on pain with the abortion procedure itself. Those studies that report on pain with osmotic dilators show that insertion is painful. Few studies have focused on the methods of pain control for laminaria or osmotic dilator insertion alone. A recent study showed that paracervical block reduced pain with osmotic dilator insertion compared to a sham block [Soon R, et al abstract SFP). Self-administered lidocaine gel is a method of pain control found to be no worse than a paracervical block for pain control during surgical abortion at gestations of less than 12 weeks. We hypothesize that self-administered lidocaine gel is no worse than paracervical block for pain control with cervical preparation.

This study seeks to compare self-administered lidocaine gel for pain control during cervical preparation (laminaria and/or osmotic dilator insertion) for D&E to paracervical block.

Objectives

Primary Objective

Pain perceived at the time of dilator insertion measured by Visual Analogue Scale (VAS) (0-100mm).

Secondary Objectives

- Pain perceived at additional time points before, during, and after the procedure (all measured by VAS (0-100mm):
 - Anticipated Pain: 30 minutes prior to procedure
 - Baseline Pain: Immediately prior to procedure
 - Dilator Insertion: Immediately following dilator insertion
 - Post-Procedure Pain: 10-15 minutes following procedure
 - Overall Pain: Assessed after procedure
- Incidence of complications
- Provider reported ease of insertion

- Global satisfaction (acceptability) of procedure

Study Drugs

Experimental Group:

Xylocaine (lidocaine HCl) is a common local anesthetic that works by stabilizing the neuronal membrane by inhibiting the ionic fluxes required for the initiation and conduction of impulses. Local anesthetics of the amide type are thought to act within the sodium channels of the nerve membrane. According to the packaging insert, anesthesia is achieved within 5 minutes, depending on the area of application, and duration of anesthesia is approximately 20-30 minutes. It is used prior to many genitourinary procedures involving mucous membranes including the urethra, anus, and vulva. While no recommended dose is known for vaginal use prior to surgical abortion, recommended doses are known for the following procedures: 20 ml for proctoscopy/anoscopy; 10 ml for female urethral anesthesia as in cystoscopy. A single maximum dosage for 2% Xylocaine jelly is not established [Blanco 1982], however Lexicomp drug information for topical lidocaine jelly cites a maximum dose of 600 mg in any 12-hour period.

The serum toxicity of intracervical lidocaine is thought to be around 5 ug/ml [Blanco 1982] and a study looking at serum lidocaine levels 10 minutes after paracervical injection of 20 ml of 1% lidocaine (200 mg total) found mean blood levels of 0.9 to 1.61 ug/ml [McKenzie 1978].

Similarly, a study investigating vaginal anesthesia with 4ml of 10% lidocaine spray (400mg total) 5 minutes prior to high dose intracavitary brachytherapy found a significant decrease in procedural pain [Chen 1998]. This study also looked at serum lidocaine levels at various time points following administration and found that the 400mg dose never reached toxic levels in participants. These data are further supported by non-toxic levels seen after nasopharyngeal and oropharyngeal application in the studies cited above.

Based on this information, participants in the lidocaine gel group will self-administer 20 ml of 2% lidocaine HCl vaginally (400 mg total) 20-30 minutes prior to the start of the procedure. We are allowing a window of time to account for real life clinic practice and possible delays.

The product:

- XYLOCAINE® JELLY 2% (lidocaine hydrochloride) AstraZeneca
 - 20 mL (20 mg/mL) – 400mg total

Control Group:

Paracervical block technique:

- Syringe loaded with 12 mL of 1% lidocaine (120 mg); 22-gauge spinal needle (x mg total)

- 2 mL injected at the tenaculum site, either 6 or 12 o'clock superficially into the cervix
- The tenaculum is immediately placed at the previously injected site
- The remaining 10 mL are slowly injected into the cervicovaginal junction in two equal aliquots at 4 and 8 o'clock; the injection is continuous from superficial to deep (1-2 cm) to superficial (injecting with insertion and withdrawal)

Study Population

Women presenting for abortion ≥ 16 weeks gestation will be invited to participate in the study protocol. This population was selected, as they typically require more dilators than the patients at lower gestational ages.

Explanation of Sample Size

Studies of patient reported pain scores indicate that the minimum, significant difference in pain score on a 100mm Visual Analogue Scale (VAS) is 13-16mm. Studies of laminaria insertion document pain scores ranging from 43-70mm, with standard deviation of 22-23. We determined Considering the continuous primary outcome and our non-inferiority hypothesis, if there is truly no difference between paracervical block and self-administered lidocaine gel for pain control with cervical preparation for D&E after 16 weeks gestation, 68 participants are required to be 80% sure that the lower limit of a one-sided 97.5% confidence interval (or equivalently a 95% two-sided confidence interval) will be above the non-inferiority limit of 15mm. Accounting for participant drop-out, we will recruit 72 women to participate in this study (significance level, alpha of 2.5%; power of 80%; standard deviation of 22; non-inferiority limit of 15).

Overview of Study Design

Recruitment and Allocation of Subjects

Subjects will be recruited from the Stanford Gynecology Clinic in Palo Alto, California. They will be identified for participation through prospective chart review. Informed consent will be obtained from a trained research coordinator. Upon agreeing to participate, subjects will be randomized through block randomization to a study arm.

Criteria for Subject Selection

Inclusion:

- Women 18 and older
- Intrauterine pregnancy ≥ 16 weeks gestation
- English speaking competency
- Willing and able to sign consent forms
- Agree to comply with study procedures

Exclusion:

- Women less than 18 years of age

- IV conscious sedation
- Known allergy to study medication (lidocaine)
- Any women not meeting inclusion criteria above will be excluded from participation

Study Procedures

This study will take place during subjects' cervical preparation visit. Following informed consent, participants will be randomized to a study group—group allocation information will be kept in a sealed, opaque envelope. Upon consenting for the study, a research coordinator will assign a unique subject ID number to the participant. This subject ID number's envelope will be opened to determine allocation. Participants, research staff, and health care provider will not be blinded to the allocation.

If the subject is randomized to the experimental group (self-administered lidocaine gel), she will be instructed on how to self-administer the gel vaginally by the study coordinator. She will insert 20ml of 2% lidocaine gel into her vagina using a pre-loaded syringe. After 15 minutes, the procedure will be begin.

If the subject is randomized to the control group (provider-administered paracervical block), cervical anesthesia and preparation will commence to standard.

For both groups, the research coordinator will collect demographic and medical history and document procedure data. For VAS scores, the research coordinator will administer the 100mm VAS on an iPad. Pain scores will taken "in real time". There is no follow-up for this study.

Data Collection

Data collection will be obtained through a REDCap survey.

Data to be collected include:

- Demographics
 - Location of procedure
 - MRN
 - Date enrolled
 - First name
 - Last name
 - Date of birth
 - Age
 - Phone number
 - Race
 - Ethnicity
- Medical History (Physical Exam and Ob/Gyn History)
 - Height
 - Weight

- BMI
- Gestational age
- Medication allergies
- Current medications
- Number of previous pregnancies
 - Number of previous vaginal deliveries
 - Number of previous cesarean sections
 - Number of previous abortions
 - Number of previous abortions after 16 weeks gestation
 - Number of miscarriages
- Medical problems
- Previous surgeries
 - Previous cervical surgeries
- Procedure Data
 - Provider type (i.e. resident, fellow, attending)
 - Provider reported ease of procedure
 - Uterine position
 - Initial cervical dilation
 - Number of osmotic dilators or laminaria placed
 - Time with lidocaine gel before tenaculum
 - Time with paracervical block before tenaculum
 - Total speculum time
 - Complications
- Procedure VAS Data
 - Anticipated
 - Baseline
 - Speculum insertion
 - Paracervical block (control group only)
 - Tenaculum placement
 - Laminaria/osmotic dilator insertion
 - Post-procedure
 - Overall pain
- Acceptability Data
 - Gel leakage acceptability (experimental group only)
 - Likelihood to recommend procedure
 - Comfort with tampons
 - Maximum time willing to wait for pain control

Data Analysis and Monitoring

Enrollment will be reviewed bi-weekly by the research team. Given that there are minimal safety risks involved in this study, we do not plan to convene an independent Data Safety Monitoring Board (DSMB).

Data Management and Storage

Data will be entered into and stored on REDCap.

Methods of Analysis

Data will be exported from REDCap to SPSS Version 23.0 for analysis.

Perioperative characteristics will be examined among the groups using chi square test and fisher's exact test, where appropriate; mean and median VAS pain scores will be analyzed with Student's *t*-tests and non-parametric tests, respectively; mean and median overall satisfaction with pain control and provider reported ease of procedure via VAS scores will be compared using Student's *t*-tests and non-parametric tests, respectively; linear regression will be completed in multivariable analysis to identify predictors of pain.

Analysis and Dissemination of Results

Analysis will occur upon completion of study enrollment. The co-investigators plan to prepare at least one manuscript for submission to a peer-reviewed journal. In addition, the co-investigators will present the results of the study at conferences and meetings where appropriate.

Risks and Benefits

Participants are not promised any benefits from participating in the study.

Potential risks associated with this study are minimal. The risk to the participants' physical, psychological, economic, or social well-being in this study is not anticipated to be any different or greater from women not participating in the study.

The risks, side effects, and discomforts of the study, whether the subject receives lidocaine gel or lidocaine paracervical block, are expected to be similar and include:

- Side effects with medications
 - Lidocaine - with numbing medicine in a woman's cervix, there is an infrequent risk of getting a unusual taste in the woman's mouth, ringing in her ears, nausea or light-headedness. Rarely, a person can have a seizure from the numbing medicine.
- Pelvic examination: Subjects may infrequently experience some discomfort during the pelvic exams
- Emotional Discomfort: Some of the questions the subject will be asked in this study may make the subject feel uncomfortable or embarrassed. She can refuse to answer any question that makes her uncomfortable or embarrassed, from any person, at any time.

Cost to the Participant and Compensation for Participation

Participants will not be compensated for their time of participation in this study. There will be no additional cost for participation in the study.

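### Low-priority improvement, not an error: taking both pre-procedure VAS scores before the envelope is opened would allow a prespecified covariate-adjusted comparison of insertion pain

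*Combined protocol and SAP*

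**What the plan says.** The Primary Objective is pain at dilator insertion on a 0-100 mm VAS. Methods of Analysis compares VAS scores with t-tests and non-parametric tests. Its only model is a multivariable linear regression meant to find predictors of pain. That model names no covariates and is not linked to the non-inferiority comparison.

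Secondary Objectives lists two scores taken before the procedure: "Anticipated Pain: 30 minutes prior to procedure" and "Baseline Pain: Immediately prior to procedure".

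On the order of events:

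- **Randomization** (Recruitment and Allocation of Subjects): "Upon agreeing to participate, subjects will be randomized through block randomization to a study arm".
- **Allocation** (Study Procedures): after consent and the assignment of an ID, "This subject ID number's envelope will be opened to determine allocation".
- **Blinding** (Study Procedures): "Participants, research staff, and health care provider will not be blinded to the allocation".
- **Gel** (Study Drugs): inserted "20-30 minutes prior to the start of the procedure", with anesthesia expected within 5 minutes. Study Procedures instead starts the procedure 15 minutes after insertion.

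Explanation of Sample Size states that "68 participants are required to be 80% sure", with "standard deviation of 22; non-inferiority limit of 15", and recruits 72.

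**The concern.** A pre-treatment score that predicts the outcome can narrow the confidence interval at no cost in participants. This trial has little slack, since it is sized at 80% power on an SD of 22 when its own cited range is 22-23. The two pre-procedure scores are the obvious candidates, but their timing is a problem.

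The baseline score is taken after active treatment in one arm and before it in the other. The anticipated score comes at or before gel insertion, so the gel itself should not affect it. However, no section places it before the envelope is opened, so a woman may already know whether she will receive gel or an injection when she rates the pain she expects. That is an unstated order, not a demonstrated contamination.

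If either score were later used to adjust the treatment effect, an effect of the gel, or of knowing the allocation, could be carried into the adjusted estimate. A variable called baseline invites that use.

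**Working it through.** **Timing, side by side**

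| Score | Gel arm | Block arm |
|---|---|---|
| Anticipated (30 min before) | At or before gel; order relative to the envelope not stated | Before block; order relative to the envelope not stated |
| Baseline (immediately before) | After gel, whether 15 or 20-30 min | Before block |

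**The plan's own sample size.** Inputs from Explanation of Sample Size: one-sided alpha 2.5%, power 80%, SD 22, margin 15, true difference 0. The allocation ratio is not stated; 1:1 is assumed.

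n per arm = 2(1.960 + 0.842)² × 22² / 15² = 33.8, rounded up to 34, or 68 in total. This reproduces the plan's figure.

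**Unadjusted analysis, 34 per arm**

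- SE = 22 × √(2/34) = 5.336 mm, with 66 degrees of freedom.
- Half-width of the 95% CI = 1.9966 × 5.336 = 10.65 mm.
- Power from the non-central t with non-centrality 15/5.336 = 2.81: 79.1%. This is slightly under 80% because the sample size formula uses the normal distribution.

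**ANCOVA with two pre-allocation scores**

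Let R be the multiple correlation of the two scores together with insertion VAS within arm. The documents do not give R, so a range is assumed. For normal covariates,

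SE = 5.336 × √(1 − R²) / √(1 − r²), with 64 degrees of freedom.

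Here r² is the chance imbalance of the covariates between arms, distributed Beta(1, 32.5). It inflates the SE by 32.5/32 = 1.0156 on average. Power is averaged over r². The half-width holds the total SD at 22. For R = 0.3 it is 1.9977 × 5.336 × 0.9539 × 1.0156 = 10.33 mm.

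| R (assumed) | Power | Half-width (mm) | Power, complete case, 32 per arm |
|---|---|---|---|
| Unadjusted, 34 per arm | 79.1% | 10.65 | – |
| 0 | 77.8% | 10.83 | 75.2% |
| 0.1 | 78.2% | 10.77 | 75.6% |
| 0.2 | 79.5% | 10.61 | 76.8% |
| 0.3 | 81.5% | 10.33 | 79.0% |
| 0.4 | 84.5% | 9.92 | 82.1% |
| 0.5 | 88.2% | 9.38 | 86.2% |

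Power and half-width both break even at R of about 0.18. At R = 0 adjustment loses 79.1 − 77.8 = 1.3 points.

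**Missing covariates.** Risks and Benefits lets a participant decline any question. The last column assumes that 2 women per arm lack both scores and are dropped. R must then be about 0.30 merely to match the unadjusted 79.1%. Filling the gaps with the mean of both arms pooled keeps all 68. In simulation (100,000 trials per R, covariates correlated 0.3, scores missing at random, all assumed), this gave 81.3% power at R = 0.3. The false non-inferiority rate at a true difference of 15 mm stayed at 2.5%.

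**If a shifted score were used instead.** The adjusted estimate moves by slope × shift. With one covariate, an assumed covariate SD of 22 and an assumed shift of 5-10 mm, the movement is 0.3 × 5 to 0.3 × 10 = 1.5-3.0 mm at a correlation of 0.3. That is 10-20% of the margin. It applies only to an adjustment that the plan does not call for.

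**The case against.** The strongest reply is that nothing here is wrong. An unadjusted comparison of randomized arms is valid, the sample size matches it, and the baseline score is listed only as a secondary time point. All of that stands.

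The benefit also rests on a correlation the documents do not supply. Below R of about 0.18 adjustment does worse, and at R = 0.3 it gains only 2.4 points of power and 0.3 mm of half-width. A score of current pain before any procedure may also have little spread and add nothing. For scale, if all 72 recruited women gave an insertion VAS, the unadjusted test at 36 per arm would have 81.4% power and a half-width of 10.34 mm, the same as ANCOVA in 68 women at R = 0.3. These points set the weight. They do not remove the option, since adjustment could be applied to 72 women as well.

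There is also a simpler route. Data Collection already lists gestational age, previous vaginal deliveries and previous cervical surgeries, which could serve as covariates without moving any question. That is a fair addition, but it does not settle the timing or the label of the VAS scores.

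Finally, Methods of Analysis never says that a confidence interval will be compared with 15 mm; only the sample size text does. That link has to be made first, with or without covariates.

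**Conclusion.** The point holds as a low-priority improvement. The planned test stands and no bias follows from it. Neither pre-procedure score can be relied on as a clean covariate as now timed: the baseline score because it follows the gel in one arm, and the anticipated score because its order relative to the envelope is not stated.

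The effect of the change runs from a loss of 1.3 points of power (R = 0) to a gain of 88.2 − 79.1 = 9.1 points (R = 0.5). This assumes 34 per arm, SD 22, no true difference, normally distributed covariates and complete scores. The timing facts rest on the text alone. The size of the gain rests wholly on the assumed R.

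**What to change.** 1. Ask the anticipated-pain and current-pain VAS after consent and before the envelope is opened, in both arms, and write that order into Study Procedures.
2. In Methods of Analysis, prespecify ANCOVA with these two scores as covariates for the gel-minus-block difference in insertion VAS, and judge its 95% CI against the 15 mm limit. Include every participant with an insertion VAS, filling a missing covariate with the mean of both arms pooled. Report the unadjusted difference and CI as a sensitivity analysis.
3. If the score immediately before the procedure is kept, report it descriptively, label it as post-gel in the gel arm, and do not use it to adjust the treatment effect.

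**Cost.** Two questions are asked earlier, and one is added if the immediate pre-procedure score is kept. The analysis plan gains two lines, for the model and the missing-covariate rule. The model spends two degrees of freedom, and up to 1.3 points of power are lost if the scores predict nothing. There are a few more answers that a participant may decline. An anticipated score taken before allocation no longer reflects expectation of the assigned method, so that secondary time point changes in meaning.

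Separately, the gel-to-procedure times in Study Drugs (20-30 minutes) and Study Procedures (15 minutes) contradict each other and must be reconciled. The baseline score follows the gel under either, so this point does not depend on the answer.

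### The only non-inferiority criterion has the wrong sign and no stated direction: a lower limit above 15 mm does not show that gel is no worse than block

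*Combined protocol and SAP*

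**What the plan says.** The Background of the combined protocol and SAP sets a non-inferiority aim: "We hypothesize that self-administered lidocaine gel is no worse than paracervical block for pain control with cervical preparation". The Primary Objective names a measurement, "Pain perceived at the time of dilator insertion measured by Visual Analogue Scale (VAS) (0-100mm", but no contrast between arms and no margin.

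Explanation of Sample Size gives the size of a meaningful difference without a sign ("difference in pain score on a 100mm Visual Analogue Scale (VAS) is 13-16mm"). It then assumes no true difference ("if there is truly no difference between paracervical block and self-administered lidocaine gel for pain control") and says that 68 participants give 80% assurance that "the lower limit of a one-sided 97.5% confidence interval (or equivalently a 95% two-sided confidence interval) will be above the non-inferiority limit of 15mm". The closing parenthesis repeats the inputs, again with an unsigned limit: "significance level, alpha of 2.5%; power of 80%; standard deviation of 22; non-inferiority limit of 15".

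Methods of Analysis says that "mean and median VAS pain scores will be analyzed with" Student's t-tests and non-parametric tests, with linear regression for predictors of pain. It gives no margin, no confidence-interval rule and no direction for the comparison.

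**The concern.** A non-inferiority rule needs a defined difference, a signed limit, and the confidence bound that must clear it. Here the bound is the lower one, the limit is a positive 15, and the difference is undefined. There are two possible readings, taking a higher VAS as more pain:

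- **Gel minus block, lower limit above +15 mm:** this shows that gel is more than 15 mm worse.
- **Block minus gel, lower limit above +15 mm:** this shows that gel is more than 15 mm better, a demanding form of superiority.

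Neither matches the hypothesis in the Background. Both also contradict the sentence they stand in, because no such rule can be met 80% of the time when the arms do not differ.

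This sentence is the only place where the plan says what result would show non-inferiority. A reader who doubts it has no correct statement to check it against. Applied as printed, it would fail a trial in which both arms had the same mean pain. Under gel minus block, it would be met only by a result showing gel to be clearly worse.

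**Working it through.** **Inputs.** From Explanation of Sample Size: one-sided alpha 2.5%, power 80%, SD 22 mm (cited range 22–23), margin magnitude 15 mm, true difference 0, 68 evaluable. Two assumptions are mine. Allocation is taken as 1:1, because Recruitment and Allocation of Subjects says only that "subjects will be randomized through block randomization to a study arm". Higher VAS is taken as more pain.

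**Step 1: reproduce the plan's figure.** n per arm = 2 × (22/15)² × (1.960 + 0.842)² = 33.77, rounded up to 34, so 68 in total. This matches the plan and confirms that 15 was used as the size of a non-inferiority margin.

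**Step 2: precision at 34 per arm.** SE = 22 × √(2/34) = 5.336 mm. With t(0.975, 66 df) = 1.9966, the 95% half-width is 1.9966 × 5.336 = 10.65 mm.

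**Step 3: the intended rule** (gel minus block, upper limit below +15 mm; the same as block minus gel, lower limit above −15 mm).
- Power at zero difference: Φ(15/5.336 − 1.96) = 80.3%, or 79.1% by noncentral t.
- Chance of passing if gel is truly 15 mm worse: 2.5%.
- Largest observed gel excess that still passes: 15 − 10.65 = 4.35 mm (3.86 mm if the SD is 23).

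**Step 4: the printed rule** (lower limit above +15 mm).
- Observed difference needed: 15 + 10.65 = 25.65 mm (26.14 mm if the SD is 23).
- Chance of meeting it at zero difference: 9.2 × 10⁻⁷ (normal) or 1.1 × 10⁻⁶ (t).
- With SD 23: 1.7 × 10⁻⁶ and 2.0 × 10⁻⁶. With a 45:23 split at SD 22: 1.9 × 10⁻⁶ and 2.3 × 10⁻⁶.

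Nothing in the cited SD range, nor a roughly 2:1 allocation, brings this near 80%.

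**Step 5: two worked results** (gel minus block, SD 22).

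| Observed difference | 95% CI | Intended rule | Printed rule |
|---|---|---|---|
| 0 mm | −10.7 to +10.7 | met | not met |
| +26 mm | 15.3 to 36.7 | not met | met |

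**Step 6: what if only a minus sign is added?** If the difference is then read as gel minus block, the rule becomes a lower limit above −15 mm. A gel truly 15 mm worse would pass with probability Φ(30/5.336 − 1.96) = 99.99% (99.98% by t), against 2.5% under the intended rule.

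**The case against.** The strongest reply is that this is an evident slip. The Background gives the direction. The sample-size section gives the hypothesis type, the size of the margin, the confidence level, a true difference of zero and 80% power, and only one rule fits all of these and reproduces 68. On this view nobody would apply the printed words, so the 25.7 mm threshold and the one-in-a-million figure only confirm a typing error. The sentence serves to justify a sample size and acts as the decision rule only by default, because Methods of Analysis is silent.

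Much of this stands. The intended rule can be inferred, and the extreme probability shows that the words cannot be what was meant; it does not measure lost power. The missing non-inferiority analysis in Methods of Analysis is a separate issue and adds no weight here. But being able to infer a success criterion is not the same as having it in writing, and the direction matters as much as the sign, as Step 6 shows. Study Procedures leaves participants, research staff and providers unblinded, which is a further reason to fix the rule in writing before results are seen.

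A second reply is that 68 is itself only approximate. That is fair. On a t basis power is 79.1%, and 35 per arm would be needed for 80%. At SD 23, power with 68 falls to 76.7% (normal) or 75.5% (t), and the formula asks for 74, more than the 72 to be recruited. This bears on the choice of SD, not on the error in the rule.

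**Conclusion.** The concern holds and must be fixed. The trial's only success criterion, as printed, does not define non-inferiority under either direction of subtraction, and no other section states a correct rule.

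The error is confined to the wording. At the plan's SD of 22, and by the normal approximation, 68 is the right number for the intended rule. Its severity comes from the sentence being the sole criterion and wrong as written, with opposite conclusions under the printed and intended rules for results such as 0 mm and +26 mm. The figures rest on 34 evaluable per arm and SD 22; the reading of better and worse rests on higher VAS meaning more pain. Using SD 23 or a 45:23 split does not change the conclusion.

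**What to change.** Replace the sentence in Explanation of Sample Size with wording such as:

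> The difference is mean VAS at dilator insertion, gel minus block. Non-inferiority is concluded if the upper limit of the two-sided 95% confidence interval is below +15 mm. If the true difference is zero and the SD is 22 mm, 68 evaluable participants (34 per arm) give about 80% power.

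The 34 per arm assumes equal allocation, which the sponsor should confirm. If the sponsor prefers to stay closer to the present text, the equivalent is block minus gel with the lower limit above −15 mm. Either way, sign and direction must be corrected together.

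Give the limit in the closing parenthesis the same sign and direction, and state the same rule once in Methods of Analysis so that the two sections agree.

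The cost is one sentence and its parenthesis, repeated once. The 68 required, the 72 recruited, the design and the conduct do not change.

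### The trial is designed for non-inferiority with a 15 mm limit, but Methods of Analysis never applies that limit and does not say which test decides

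*Combined protocol and SAP*

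**What the plan says.** Background sets the hypothesis: "We hypothesize that self-administered lidocaine gel is no worse than paracervical block for pain control with cervical preparation". Primary Objective names the outcome: "Pain perceived at the time of dilator insertion measured by Visual Analogue Scale (VAS) (0-100mm").

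Explanation of Sample Size is explicit about the design: "Considering the continuous primary outcome and our non-inferiority hypothesis". It gives the parameters ("significance level, alpha of 2.5%; power of 80%; standard deviation of 22; non-inferiority limit of 15") and states the condition to be met with 80% probability: "the lower limit of a one-sided 97.5% confidence interval (or equivalently a 95% two-sided confidence interval) will be above the non-inferiority limit of 15mm".

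Methods of Analysis then deals with every VAS pain score in one clause: "mean and median VAS pain scores will be analyzed with Student's *t*-tests and non-parametric tests, respectively". It does not mention the 15 mm limit, a confidence interval, the primary time point, or which of the two kinds of test settles the primary question. Satisfaction and ease of procedure are handled in the same form. No other section supplies these elements for the analysis.

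**The concern.** A non-inferiority claim rests on whether the confidence interval for the difference excludes the margin. A standard t-test, or a non-parametric test with no shift by the margin, asks whether the difference is zero. Its p-value does not show whether a 15 mm disadvantage has been ruled out. An analyst who follows Methods of Analysis literally would therefore report a result that does not answer the question the trial was sized for.

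Two features make this worse. Two families of tests are listed with no order between them, and allocation is open to participants, staff and providers, so the deciding analysis could be chosen after results are seen. Also, the only place where the criterion appears states it in a form that cannot be used: a lower limit above 15 mm.

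**Working it through.** **Inputs.** Margin 15 mm, SD 22 mm, one-sided alpha 2.5%, power 80%, true difference 0, 68 required and 72 recruited (all from Explanation of Sample Size). The same section cites SDs of 22-23, so both are used. The allocation ratio is not stated; 1:1 is assumed, giving 34 to 36 per arm. Scores are treated as normal. The difference is gel minus block, and a positive value means more pain with gel.

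**1. Reproduce the plan's figure.** n per arm = 2 × (z₀.₉₇₅ + z₀.₈₀)² × SD² / margin² = 2 × (1.960 + 0.842)² × 22² / 15² = 33.77 (unrounded quantiles), rounded up to 34 per arm, or 68 in total. This matches. The same formula would also size a two-sided 5% superiority test for a 15 mm difference, so the number shows that a 15 mm comparison of means was intended. It is the section's wording that makes it non-inferiority.

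**2. Where each rule changes its answer (34 per arm, SD 22).**
- SE = 22 × √(2/34) = 5.336 mm
- t(0.975, 66 df) = 1.9966
- Half-width of the 95% CI = 1.9966 × 5.336 = 10.65 mm
- Non-inferiority requires difference + 10.65 < 15, so a difference below 4.35 mm
- The zero-difference t-test is non-significant for differences up to 10.65 mm in either direction
- At 4.35 mm the two-sided t-test p-value is 0.418

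**3. Over the plausible range.** The last column is the probability that the t-test gives p > 0.05 when gel is truly 15 mm worse (noncentral t).

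| Per arm / SD | Half-width (mm) | Non-inferiority cut-off (mm) | t-test p at cut-off | P(p > 0.05) at true 15 mm |
|---|---|---|---|---|
| 34 / 22 | 10.65 | 4.35 | 0.418 | 0.209 |
| 34 / 23 | 11.14 | 3.86 | 0.491 | 0.245 |
| 36 / 22 | 10.34 | 4.66 | 0.372 | 0.186 |
| 36 / 23 | 10.81 | 4.19 | 0.442 | 0.221 |

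In all four settings the CI rule wrongly declares non-inferiority at a true 15 mm difference with probability 0.025, as designed.

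**4. Three possible results (34 per arm, SD 22).**

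| Observed difference (mm) | t-test p | 95% CI (mm) | Against the 15 mm limit |
|---|---|---|---|
| 4 | 0.456 | -6.65 to 14.65 | Non-inferior |
| 5 | 0.352 | -5.65 to 15.65 | Not shown |
| 10 | 0.065 | -0.65 to 20.65 | Not shown |

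All three are non-significant, and only the first meets the criterion.

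**5. How often the rules diverge (34 per arm, SD 22).** At a true difference of 5 mm the t-test is non-significant in 84.8% of trials and non-inferiority is shown in 45.5%. At 10 mm the figures are 54.5% and 15.0%. At either value, about 40% of simulated trials are non-significant and also fail non-inferiority.

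**6. Direction of the stated limit.** Higher VAS means more pain. For gel minus block, a lower limit above +15 would show gel to be worse by more than 15 mm. For block minus gel, it would show gel to be better by more than 15 mm. Neither is non-inferiority. The usable forms are an upper limit of gel minus block below +15, or a lower limit of block minus gel above -15.

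**The case against.** The strongest reply is that this is one short document and Explanation of Sample Size already contains the margin, alpha and CI level, tied to a non-inferiority hypothesis. The 95% CI it refers to comes from the same two-sample t procedure that Methods of Analysis names. On that view the analysis section is silent rather than contradictory, the pairing of means with t-tests points to the t procedure as primary, and only a cross-reference is missing. Methods of Analysis states no null hypothesis and does not say that a non-significant result will be read as showing gel to be no worse. The slip in direction is recoverable, since the calculation assumes zero true difference and returns exactly 68.

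Much of this is right on the facts. The criterion does exist in the document, the t procedure can deliver it, and the intent can be inferred. The false-claim rate of about 21% applies only under a reading the documents do not state, so it is an illustration and not a prediction. The VAS clause also covers secondary time points, where an ordinary comparison is unobjectionable.

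The defect remains. The sample-size text describes what the numbers are meant to assure; it does not prescribe an analysis. Taken literally, its rule gives a wrong threshold. Nothing in the document says that the primary outcome will be compared with 15 mm, and nothing ranks the two kinds of test. A reader following the plan reaches either a test of a different question or an incorrect decision rule.

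**Conclusion.** The concern holds, and the plan is wrong as written on its primary conclusion. Over 34-36 per arm and SD 22-23, the non-inferiority cut-off is an observed difference of about 4.3 mm (3.9-4.7), while the t-test stays non-significant up to about 10.7 mm (10.3-11.1). Results between those values would be reported as showing no significant difference although the trial had missed its own criterion. At the cut-off the t-test p-value is about 0.42 (0.37-0.49), so the 0.05 threshold does not mark it. If non-significance were taken to mean no worse, the error rate at a true 15 mm difference would be about 21% (18.6-24.5%) instead of 2.5%. These figures assume 1:1 allocation and normal scores. That a zero-difference test does not address the margin depends on neither assumption. The sample-size arithmetic itself is sound. This must be fixed before the data are analysed.

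**What to change.** Add to Methods of Analysis: *The primary analysis is the difference in mean dilator-insertion VAS (gel minus block) with its two-sided 95% CI from the two-sample t procedure. Non-inferiority is concluded only if the upper limit is below +15 mm. The non-parametric comparison of the primary outcome is supportive.*

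In Explanation of Sample Size, reword the confidence-limit statement to match: upper limit of gel minus block below +15 mm.

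The cost is two or three sentences and one corrected phrase. The margin, alpha, CI level and t procedure are already in the document, and the 68 required, the 72 recruited and the data collected stay as they are.
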